2.5 Statistical Assessment of the Study Objectives

The efficacy endpoints will be summarized within the FAS using descriptive statistics by time point and treatment. For the primary and key secondary endpoints these statistics will include 95% confidence intervals for the treatment difference. Testing will also be used for the primary and key secondary endpoints.

2.5.1 Primary Analysis

The difference in the primary efficacy outcome measure (WI-NRS change from baseline to Week 6) between treatment groups will be tested using an analysis of variance (ANOVA) model controlling for the stratification factors. A main effects model with an interaction term (treatment by stratification factors) and a Type II hypothesis will be used. More precisely this ANOVA model uses the following as a stratified adjusted measure of the change from baseline for a given treatment group:

$$\Delta = \sum_{j=1}^4 \frac{n_{1j}n_{2j}}{n_{1j}+n_{2j}} \Delta_j ,$$

where j represents the stratification cells, n is the sample size for treatment 1 and 2 and Δ_j is the change measure for stratum j . Should a site make an error during randomization and select the wrong stratification factor (e.g. select the White stratification cell for a non-White subject) the test will use how the subject was randomized. All other summaries of race (e.g. baseline characteristics or subgroup analyses) will be based upon the correct race group and not the as randomized group.

Conceptually the hypotheses being tested for this study are:

$$H_0: \Delta_{Placebo} \geq \Delta_{Serlopitant} \quad H_a: \Delta_{Placebo} < \Delta_{Serlopitant}$$

where $\Delta_{Placebo}$ is the placebo change from baseline to Week 6 and $\Delta_{Serlopitant}$ is the similar measure for serlopitant. Each serlopitant treatment group (1 mg and 5 mg) will be compared to placebo separately.

The primary endpoint will utilize the analysis windows outlined in [Section 2.4](#), the confounding rules outlined in [Section 2.6](#) and the missing data rules outlined in [Section 2.7](#).

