2.5.2 Secondary Analyses

The differences between treatment groups for the key secondary endpoints will be tested using the same ANOVA model as used for the primary endpoint (change in ItchyQoL) or a Cochran Mantel Haenszel (CMH) test (WI-NRS 4-point responder rate) controlling for the 'as randomized' stratification factors. A CMH test will also be conducted for the WI-NRS 3-point responder rate, AI-NRS 4-point responder rate, and AI-NRS 3-point responder rate.

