2.8 Sensitivity Analyses, Subgroups and Covariates

Descriptive statistics for the change in WI-NRS at Week 6 will be provided for the subgroups indicated below. Forest plots of the difference and confidence interval for this difference will also be created. The subgroups include,

- Sex
- Age Group (< 18 years, 18 to 64 years, > 64 years)
- Race
 - All race groups with less than 30 subjects will be combined with 'Other'
 - A White versus Non-White comparison will be made
- Baseline WI-NRS
- Baseline IGA-AD
- Use of allowed concomitant medications as outlined in Section 5.7.1 of the protocol
- Treatment completion (completed treatment, did not complete treatment).

To investigate the impact of missing data / confounding sensitivity analyses will be performed for the WI-NRS endpoint. These methods include,

1. Multiple imputation, MI, methods will be used to recalculate the p-values at Week 6.
2. The summary statistics will be produced where the missing data is imputed using
 - a. Data after the confounding event are excluded with no imputation

- b. Last Observation Carried Forward (LOCF),
- c. Baseline Observation Carried Forward (BOCF).

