3.3 Clinical Study Subjects

3.3.1 Subject Disposition and Analysis Populations.

The number of subjects randomized, treated, and discontinued early, will be summarized within all randomized subjects. The reason for early termination will be summarized. Additionally, a summary of subjects present at each visit as determined by the presence of a vital signs result, will be provided.

A listing of entry criteria that were not met will be produced. The listed criteria will include the criteria language. A table of the violated entry criteria for randomized subjects will be produced as well as a table that summarizes the screen failure reasons for screen failure subjects.

The number of subjects in each analysis population will be summarized.

3.3.2 *Demographics and Baseline Characteristics*

Demographic and baseline characteristics will be summarized descriptively by treatment group. This will include the following items:

1. Demographic variables

- a. Age
- b. Race
- c. Ethnicity
- d. Sex
- e. Height
- f. Weight
 - Baseline WI-NRS
 - Presence or absence of active AD
 - Baseline IGA-AD
 - Age at AD diagnoses
 - AD severity relative to prior 3 and 12 months
 - Family history of atopy (eczema, asthma, allergic rhinitis)
 - Prior Treatments of AD (e.g. antibiotics, antihistamines, corticosteroids, biologics, immunomodulatory agents)

3.3.3 *Concomitant Medications and Procedures*

Medications and procedures with a stop date before the treatment dosing date will be considered prior medications/procedures. Medications/procedures with a start or stop date on or after the treatment dosing date will be considered concomitant. All medications/procedures marked as ongoing are concomitant.

A medication/procedure with an incomplete stop date will be considered concomitant if:

1. Month is missing and year is equal to or after the year of treatment dosing date
2. Day is missing and year is equal to the year of the treatment dosing date and month is equal to or after the month of the treatment dosing date.

All concomitant medications will be summarized by treatment group. All medications, including prior medications, will be provided in listings.

A table and listing will be produced to summarize confounding events as defined in [Section 2.6](#).

A table and listing will be produced to summarize the allowed concomitant medications (antihistamines, topical steroids, topical calcineurin inhibitors, emollients).

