The WI-NRS endpoints (result, change from baseline, percent change from baseline, 3-point and 4-point responders) will be summarized at the primary time point, Week 6, as well as at Week 2, 4 and Follow-up. The summary measures will include 95% Wald confidence intervals for the treatment difference. The baseline WI-NRS will also be summarized, though no confidence interval will be produced. A graph of the mean WI-NRS results and change from baseline results by timepoint and treatment will be produced as well as a cumulative distribution function plot (CDF plot) of the Week 6 results.

The WI-NRS scores for days -7 to 14 will be plotted by averaging the available data across subjects within treatment group and study day. These results will be summarized in a table along with change from baseline where baseline is defined in the identical manner used for the weekly measures, see [Table 4](#).

The summary measures for the WI-NRS change from baseline results and the 4-point responder rate will be produced using four endpoint derivation methods, one primary method and three sensitivity measures. The difference between these methods is how the weekly measures are calculated. The primary derivation method uses all reported data prior to use of excluded therapy or changes to allowed adjunctive therapies and the missing data imputation rules outlined in [Section 2.7](#). Sensitivity analyses as defined in [Section 2.8](#) will also be conducted.

Testing will be used for the change from baseline and 4-point responder rates endpoints at Week 6. The test used for the 4-point responder rate (primary endpoint) is a CMH test controlling for the 'as randomized' stratification factors. The 'as randomized' stratification factors are based upon the stratification cell the subject was randomized to. The differences

between treatment groups for the change from baseline measure will be tested using an ANOVA model controlling for the stratification factors. A main effects model with an interaction term (treatment by stratification factors) and a Type II hypothesis will be used. Each serlopitant treatment group (1 mg and 5 mg) will be compared to placebo separately and the multiplicity rules outlined in [Section 1.6](#) will be used to interpret these p-values.

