‘Sensitivity’ p-values will be constructed using multiple imputation (MI) methodology. This approach imputes randomly generated values instead of the fixed value. Using the example from [Section 2.6](#) (i.e. a subject had data up to Week 4 but is missing their Week 6 results: $\Delta_4 + \Delta_{(4,6)}$), at least 1,000 random realizations of $\Delta_{(4,6)}$ will be generated using code similar to the following,

```
proc mi nimpute=1000;  
class trt;  
monotone reg(x);  
var trt x;
```

From these realizations of $\Delta_{(4,6)}$ the change from baseline to Week 6 will be calculated. Hence, there will be at least 1,000 random realizations of the responder status. The p-value from the MI analysis will be calculated using the SAS software procedure `mianalyze`.

Finally, the change in WI-NRS results will be summarized within the subgroups outlined in [Section 2.8](#). Forest plots based upon the same subgroups will also be produced.

3.4.3 *ItchyQol*

The ItchyQol endpoint will be summarized at Baseline, Week 2, 4, 6 and Follow-up. The summary measures will include 95% Wald confidence intervals of the treatment difference. In addition, a graph of the mean score by treatment and timepoint will be produced along with a graph of change from baseline. The difference between serlopitant 1 mg and 5 mg individual versus placebo at Week 6 will be tested with the identical ANOVA model as used for the change from baseline WI-NRS endpoint.

3.4.4 *Additional and Exploratory Endpoints*

The additional and exploratory endpoints (AI-NRS, sPGA, IGA-AD, 5-D Pruritus Scale, Actigraphy endpoints) will be summarized at baseline, Week 2, 4, 6 and Follow-up. The result as well as change from baseline will be summarized. The PGIC endpoint is a change measure so only the results at each time point will be summarized. As the 5-D Pruritus Scale was introduced into the study part way through the study, only subjects with a baseline value will be included in the summary table.

For the IGA-AD endpoint a separate analysis will be performed where the result is dichotomized to responder/non-responder. This measure will be summarized at Week 2, 4, 6 and Follow-up and be limited to subjects with a mild or greater assessment at baseline.

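### The models for change in WI-NRS and change in ItchyQoL leave out the baseline score; the tests are valid without it, but adding it would give a small gain in precision at low cost

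*SAP*

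**What the plan says.** - **Primary model.** SAP 2.5.1 lists treatment, the stratification factors (sex and race, four cells) and their interaction: "A main effects model with an interaction term (treatment by stratification factors) and a Type II hypothesis will be used". It then gives a stratum-weighted formula, introduced by "More precisely this ANOVA model uses the following as a stratified adjusted measure of the change from baseline for a given treatment group". Protocol 8.8 has the same model and formula, and the protocol synopsis has the model. SAP 3.4.2 repeats that differences "between treatment groups for the change from baseline measure will be tested using an ANOVA model controlling for the stratification factors".
- **ItchyQoL.** SAP 2.5.2 has this key secondary endpoint "tested using the same ANOVA model as used for the primary endpoint (change in ItchyQoL"), and SAP 3.4.3 repeats it.
- **Planned uses of baseline WI-NRS.** It is one of the subgroups in SAP 2.8, with descriptive statistics and forest plots of the treatment difference. It is a baseline characteristic in SAP 3.3.2 ("Demographic and baseline characteristics will be summarized descriptively by treatment group"). It is tabulated in SAP 3.4.2 ("The baseline WI-NRS will also be summarized, though no confidence interval will be produced").
- **Sensitivity analyses.** The title of SAP 2.8 mentions covariates, but the section names no covariate adjustment. Its stated purpose is limited: "To investigate the impact of missing data / confounding sensitivity analyses will be performed for the WI-NRS endpoint".
- **Multiple imputation.** SAP 3.4.2 says that the random increments "will be generated using code similar to the following"; the code shown contains only treatment and the increment.

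**The concern.** A change score fixes the slope of the Week 6 score on baseline at 1. If the true slope is lower, two things follow. The residual variance is larger than it needs to be. Also, (1 - slope) times any chance baseline difference between arms within strata stays in the treatment estimate.

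Protocol 3.2 gives possible variation in baseline itch by gender and race as a reason for stratifying. The strata may therefore absorb some baseline variance, but not the part within cells.

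At stake is precision on the primary endpoint, chiefly at the one-sided 2.5% level that SAP 1.6 treats as the generally accepted standard of evidence. Precision on ItchyQoL, the last step of the testing sequence within each dose, is at stake too. The planned tables would show a baseline imbalance, but an adjustment added after seeing one would be post hoc.

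**Working it through.** **Inputs from the documents.** 150 per arm, difference 1, SD of change 2.9, t-test, one-sided 5%, and the 2.5% level as an additional standard (SAP 1.6). Average weekly WI-NRS of at least 6 in each screening week (protocol 4.2) on a scale ending at 10 (SAP 2.3.2).

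**Assumptions, not in the documents.** Baseline SD *s* of 0.9 to 1.155; the upper value is a uniform distribution on 6 to 10, 4/√12 = 1.155. Slope *b* of Week 6 on baseline of 0.3 to 0.7.

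**Step 1: the plan's own figure.** Noncentral t, 298 df, noncentrality 1/(2.9 × √(2/150)) = 1/0.335: power is 90.9% at one-sided 5% and 84.5% at 2.5%. The stated 90% reproduces; 145 per arm would be enough for it.

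**Step 2: validity without baseline.** In 4,000 simulated trials under the null (four strata, additive model, baseline uniform on 6 to 10), one-sided type I error was 5.2% both without and with baseline. The Monte Carlo standard error is about 0.3 points.

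**Step 3: WI-NRS variance cut.** Cut = (1 - b)² × s² / 2.9², with 2.9² = 8.41.

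| s | b = 0.3 | b = 0.5 | b = 0.7 | b = 1 |
|---|---|---|---|---|
| 0.9 | 0.397/8.41 = 4.7% | 0.203/8.41 = 2.4% | 0.073/8.41 = 0.9% | 0 |
| 1.155 | 0.654/8.41 = 7.8% | 0.333/8.41 = 4.0% | 0.120/8.41 = 1.4% | 0 |

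If the strata already explain 10% of baseline variance, the 0.9-7.8% range becomes 0.8-7.0%; at 20% it becomes 0.7-6.2%.

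**Step 4: power with the covariate.** Residual SD = 2.9 × √(1 - cut). Over the range 0.9-7.8%, power is 91.1-92.8% at 5% and 84.8-87.3% at 2.5%. The equivalent sample size is 150/(1 - cut) = 151.3 to 162.6 per arm, or about 1 to 13 extra subjects.

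A simulation of the planned model with its interaction and Type II test (s = 1.155, strata explaining 10% of baseline variance, 6,000 runs) agrees. At 2.5%, power without and with baseline was 84.8% and 87.2% (b 0.3), 85.1% and 86.4% (b 0.5), and 84.6% and 85.2% (b 0.7).

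**Step 5: wider assumptions.** With s from 0.8 to 1.3 and b from 0.75 down to 0, the cut runs from 0.5% to 20% and power at 5% from 91.0% to 95.4%. The top needs both a wide baseline distribution and a Week 6 score unrelated to baseline.

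**Step 6: chance imbalance.** The SE of the baseline difference is s × √(2/150) = 0.104 to 0.133. A one-SE imbalance leaves (1 - b) times this in the estimate: 0.3 × 0.104 = 0.03 up to 0.7 × 0.133 = 0.09 points. The SE of the treatment difference is 0.335 and the design effect is 1.

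**Step 7: ItchyQoL.** With r the correlation of baseline and Week 6 scores, and k the Week 6 SD divided by the baseline SD, the cut is (1 - kr)²/(1 + k² - 2kr). It is zero when kr = 1 and grows as kr moves away from 1. The documents give neither r nor k, nor any ItchyQoL SD, so no figure follows from them.

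**The case against.** The strongest case against is that nothing is broken. The trial meets its stated power, type I error is unaffected, and at the study's own 5% level the gain is 0.2 to 1.9 power points. The change score already removes part of any imbalance. The forest plots will show treatment differences by baseline WI-NRS level. Every size above rests on assumed inputs. A change to the primary model needs a protocol amendment. All of this stands, and it limits the point to an improvement. The forest plots do not replace adjustment, because they give no pooled, baseline-adjusted estimate or test.

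Stronger readings that the documents do not support:
- *The primary test is biased or underpowered without baseline.* Steps 1 and 2 show otherwise.
- *ItchyQoL stands to gain a great deal because it has no entry threshold.* The missing threshold removes one reason for a small gain, but nothing in the documents fixes its size.
- *A sensitivity analysis would bring the same benefit.* It would leave the p-values in the SAP 1.6 decision rule as they are.
- *Adding baseline to the imputation code would align it with the analysis model.* That model also has strata and a treatment-by-strata interaction, and the code has no strata.

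**Conclusion.** The omission is confirmed for both endpoints in both documents, and no planned analysis adjusts for baseline. It is a small, inexpensive gain in precision forgone, not an error.

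For WI-NRS the expected benefit is about 1 to 8% of variance. In power, that is 0.2 to 1.9 points at one-sided 5% and 0.3 to 2.8 points at 2.5%, given a baseline SD of 0.9 to 1.155 and a slope of 0.3 to 0.7. It vanishes at a slope of 1. The gain is limited because entry confines baseline to roughly four points of the scale while the SD of change is 2.9. For ItchyQoL the size is unknown. The change is worth making because the baseline scores are already collected and the statistical cost is negligible.

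**What to change.** Before unblinding:

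1. Add baseline WI-NRS to the primary model and baseline ItchyQoL to the ItchyQoL model as continuous covariates. Keep the strata, the interaction and the Type II test. Take the treatment difference and its 95% CI from the same model.
2. State in SAP 2.5.1 and protocol 8.8 that the stratum-weighted formula describes the unadjusted estimator.
3. Align SAP 2.5.2, 3.4.2 and 3.4.3 and the protocol synopsis.
4. If the multiple-imputation sensitivity analysis is meant to match the analysis model, put both baseline WI-NRS and the strata in its imputation model.

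**Cost.** One degree of freedom per model and no new data. No subject is lost, since anyone with a change score has a baseline. The SAP edits are short. Protocol 8.8 and the synopsis need an amendment with sponsor approval and investigator signatures (protocol 9.1). The sponsor should also decide whether the change falls under the IRB/EC approval clause there.

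**Fallback.** Keep the primary model and add a prespecified baseline-adjusted analysis to SAP 2.8. This needs SAP text only. It checks robustness to baseline imbalance but does not raise the power of the decision-rule tests.

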2.5.2 Secondary Analyses

The differences between treatment groups for the key secondary endpoints will be tested using the same ANOVA model as used for the primary endpoint (change in ItchyQoL) or a Cochran Mantel Haenszel (CMH) test (WI-NRS 4-point responder rate) controlling for the 'as randomized' stratification factors. A CMH test will also be conducted for the WI-NRS 3-point responder rate, AI-NRS 4-point responder rate, and AI-NRS 3-point responder rate.

2.6 Confounding Event

The use of excluded therapies / procedures or clinically significant changes in the dose or frequency of allowed adjunctive therapies can result in a change in pruritus. In the statistical plan the use of excluded therapies / procedures or clinically significant changes in the dose or frequency of allowed adjunctive therapies is called a confounding event. Short treatment (up to 3 days) of an excluded medication for indications other than atopic dermatitis or pruritus (see protocol for specific medications) is not considered a confounding event. Should a confounding event occur, the cause of changes in pruritus can no longer be clearly attributed to the randomized treatment. As such, the results from the WI-NRS/AI-NRS following this confounding event (i.e. on the day the confounding event occurred or after) will not be included in the analysis.

Confounding events will be identified by a blinded clinical review of the concomitant medication and procedures data prior to database lock.

2.7 Handling of Missing Data

Summary statistics will generally be reported based upon observed data. Should a determination of treatment period (on treatment, pre-treatment) be required for adverse events or concomitant medication but the corresponding date is missing, or is a partial date,

the event/medication will be considered on treatment unless the portions of the data that are available indicate this is not possible.

If a subject fails to complete their eDiary for a week or more, or a confounding event occurs the WI-NRS and AI-NRS endpoints, including the primary endpoint, may be missing. In this case, their change from baseline value will be imputed. The subject's data prior to confounding will be used. From that point forward their trajectory will be imputed based upon the trajectory of their treatment group. The imputation approach first determines the average change for each time point (i.e. Weeks 2, 4, 6) for each treatment group. The difference between weeks n-1 and n will be considered the change for Week n. These change measure will be used to 'fill in' the missing weeks between the last completed week (pre-confounding) and Week 6. Hence, a placebo subject who receives excluded therapy in Week 4 will have their Week 6 WI-NRS change from baseline imputed as $\Delta_4 + \Delta_{(4,6)}$, where Δ_4 is the observed change from baseline result for the subject up to Week 4 and $\Delta_{(4-6)}$ is the placebo change from Week 4 to 6 (i.e. the average placebo decrease from Week 4 to 6).

Missing data imputation will only be used for the WI-NRS and AI-NRS endpoints.

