4. Average weekly WI-NRS score ≥ 6 for each week of the screening period, as recorded in the eDiary.
5. Diagnosis of atopic dermatitis, as defined by the 2014 American Academy of Dermatology (AAD) Guidelines of Care for the Management of Atopic Dermatitis.¹
 - a. Subjects with active atopic dermatitis skin involvement must have had stable skin disease, defined as experiencing no disease flares, for at least 4 weeks immediately prior to randomization. Subjects using stable doses of bland emollients, topical calcineurin inhibitors, and/or low- to mid-potency topical corticosteroids at the initial Screening visit must be willing to continue these at the same doses and frequencies throughout the study.
 - b. Subjects without active atopic dermatitis skin involvement must have had a past diagnosis of atopic dermatitis, supported by written records documenting the presence of features consistent with the 2014 AAD Guidelines.
6. All female subjects who are of childbearing potential must practice highly effective contraception (i.e., pregnancy prevention method with a failure rate of $< 1\%$ per year) from the time of the initial Screening visit until 4 weeks after last dose of study drug. All fertile male subjects, with partners who are females of childbearing potential, must use condoms from randomization until 4 weeks after last dose of study drug. All subjects who are fertile males or females of childbearing potential must also refrain from sperm/egg donation starting from first dose of study drug and until 4 weeks after last dose of study drug. Please refer to [Section 7.1.5](#) for acceptable methods of contraception.
7. Weight ≥ 32 kg at the baseline visit.
8. Willing and able to complete once-daily eDiary entries within a consistent timeframe for the duration of the study.
 - a. Subjects must have $\geq 80\%$ eDiary completion rate during the screening period.
9. Judged to be in good health in the investigator's opinion.

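### The primary analysis tests fixed, imputed Week 6 WI-NRS changes as if they were observed, so the standard error that governs the step-down is usually slightly too small

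*SAP*

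**What the plan says.** **Imputation rule.** SAP 2.7 and protocol 8.2 apply when the diary lapses for a week or more, or after excluded therapy or a clinically significant change in adjunctive therapy. They keep the subject's own earlier change: "From that point forward their trajectory will be imputed based upon the trajectory of their treatment group". The worked example in both documents is the Week 4 change plus the placebo mean change from Week 4 to Week 6, which is one number.

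**Data removed by design.** SAP 2.6 states that WI-NRS results "following this confounding event (i.e. on the day the confounding event occurred or after) will not be included in the analysis".

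**Primary test.** SAP 2.5.1 applies the Section 2.7 rules to the primary endpoint, which "will be tested using an analysis of variance (ANOVA) model controlling for the stratification factors". SAP 3.4.2 confirms the order: "The primary derivation method uses all reported data prior to use of excluded therapy or changes to allowed adjunctive therapies", together with the Section 2.7 imputation. Neither document adjusts the variance for imputation. Under SAP 1.6 this p-value decides whether testing moves from 5 mg to 1 mg, and to the key secondary endpoints within each dose.

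**MI.** SAP 2.8 lists it among the sensitivity analyses: "Multiple imputation, MI, methods will be used to recalculate the p-values at Week 6". SAP 3.4.2 explains the difference: "This approach imputes randomly generated values instead of the fixed value". It labels the results as sensitivity p-values. SAP 2.8 also plans summaries with no imputation, LOCF and BOCF.

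**The concern.** An imputed value omits the subject's own Week 6 departure from the arm's average path, and every imputed subject in the arm shares the same estimated increment. The ANOVA nevertheless counts each such value as an independent observation. The information in the data is overstated, so the SE tends to be too small, the 95% interval too narrow and the p-value too low.

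This test opens the hierarchy for each dose. SAP 1.6 also attaches a claim of generally accepted evidence to the 2.5% threshold. If the fixed-value test passes a threshold and the MI version does not, the plan lets the fixed-value result stand.

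**Working it through.** **1. The plan's own figure.** Inputs from SAP 1.6: 150 per arm, difference 1, SD 2.9, one-sided 5%. SE = 2.9 × √(2/150) = 0.335, and 1/0.335 = 2.99. Power by the noncentral t is 90.9%, which agrees with the stated 90%. No imputed share enters that calculation.

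**2. Assumed inputs.** The documents give no imputed share (p), no correlation between the last-window change and the Week 6 change (r), and no ratio of last-window SD to Week 6 SD (k). I take:
- the null hypothesis, data missing completely at random, and Week 6 SD 2.9;
- p = 5%, 10% or 20%;
- last data at Week 4: SD 2.6 or 2.9, r 0.7–0.9;
- last data at Week 2: SD 2.1 or 2.9, r 0.45–0.75.

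**3. Formula.** Take the increment from subjects with both windows (paired). The arm mean after imputation is then the observed Week 6 mean plus p times the difference in last-window means between imputed and observed subjects.
- True variance: SD6² (1 + pk² − 2prk) / [n(1−p)]
- Variance the ANOVA reports: about SD6² [(1−p) + pk²] / n
- (reported SE / true SE)² = (1−p)[(1−p) + pk²] / (1 − 2prk + pk²)
- Actual one-sided error at nominal 5%: P(Z > 1.645 × SE ratio)

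Example: p = 0.10, r = 0.7, k = 2.6/2.9 = 0.897. The numerator is 0.9 × (0.9 + 0.0804) = 0.882. The denominator is 1 − 0.1255 + 0.0804 = 0.955. The SE ratio is √0.924 = 0.961, and P(Z > 1.581) = 5.7%.

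**4. A second reading of the increment.** SAP 2.7 can also mean the difference between arm means of all available data at each time point. The true variance is then SD6² [1/(1−p) + p(1−p)k² − 2prk] / n. At p = 0.20, k = 1, r = 0.45 the paired form gives 7.26% and this form 6.90%. The two can therefore differ by up to about 0.4 point at 20% imputed.

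**5. Results.** Ranges cover both readings; error is shown at nominal 5% / 2.5%.

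| Imputed | All last seen at Week 4 | SE understated | All last seen at Week 2 | SE understated |
|---|---|---|---|---|
| 5% | 5.1–5.3% / 2.6–2.7% | 0.5–2% | 5.2–5.6% / 2.6–2.9% | 1–3% |
| 10% | 5.2–5.7% / 2.6–3.0% | 1–4% | 5.4–6.3% / 2.8–3.4% | 2–7% |
| 20% | 5.4–6.5% / 2.8–3.6% | 2–8% | 5.9–7.8% / 3.1–4.6% | 5–14% |

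The Week 2 maxima need SD 2.1 and correlation 0.45.

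**6. When the direction reverses.** In the paired form the SE is too small only if rk < 1 + p(k² − 1)/2. At 10% imputed it reverses once the Week 4 SD exceeds 3.27 (r 0.9), 3.75 (r 0.8) or 4.42 (r 0.7), against 2.9 at Week 6. For example, k = 1.15 with r = 0.9 gives 4.97%.

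**7. Simulation check.** The four-stratum ANOVA was run on 20,000 null trials per scenario (Monte Carlo SE about 0.1 point), with last data at Week 4 or evenly split between Weeks 2 and 4. Error at nominal 5% was 5.1–5.5% (5% imputed), 4.9–5.9% (10%) and 5.6–7.1% (20%). The 4.9% lies a little under the closed-form floor of 5.2%, so at 10% the excess can be too small to see.

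**8. Remedy check.** 4,000 trials per scenario, 20 imputations, Rubin's rules, 10% and 20% imputed. Sequential regression on treatment, stratum and earlier changes gave 4.5–5.5% / 2.2–2.8%. Treatment-only increments, as in the SAP 3.4.2 code but extended to two steps, gave 3.1–5.2% / 1.3–2.7%. They also spread the imputed Week 6 values too widely in most scenarios (SD 2.8–4.4).

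**The case against.** **The size is assumed, and the plan limits the imputed share.** This stands. Protocol 4.2 requires at least 80% "eDiary completion rate during the screening period". The diary runs daily through follow-up, and SAP 2.4 extends the Week 6 window to Day 46. SAP 3.4.1 averages whatever days a window holds. Protocol 6.5.9 schedules a Day 40–46 visit for subjects who stop before Day 15, and stopping study drug is not in itself a confounding event. The share is still not zero by design: a confounding event on or before Day 36 empties the whole Week 6 window.

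**The sensitivity analyses already cover this.** In part. A reader might infer that the plan ignores imputation uncertainty. It does not: the MI p-values and the no-imputation summary would show a divergence, and the latter gives a valid interval if data are missing completely at random. But neither governs the step-down, and no rule says what follows if they disagree with the primary test.

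**Two stronger readings are not supported.** One is that the SE is always too small; step 6 shows the exception, although nothing in the documents suggests that pattern of SDs. The other is serious inflation. If no imputed subject had any earlier window and each started from zero change (an assumption; the plan states no rule for them), the SE ratio would be 1 − p, giving 6.9% at 10% and 9.4% at 20%. That is an upper bound, and nothing in the documents makes it likely.

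**MI by regression changes more than the SE.** This also stands, and the cost below includes it.

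**Conclusion.** The concern holds, with a modest effect. The governing SE is usually too small and the one-sided error usually slightly above 5% and 2.5%. With last data at Week 4, the excess at the 5% level is at most about 0.3, 0.7 and 1.5 points for 5%, 10% and 20% imputed. It reaches about 1.3 points at 10% and 2.8 points at 20% only if every imputed subject was last seen at Week 2, with low SD and low correlation.

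The mechanism follows from the text. The size rests on assumed shares, SDs and correlations, and on data missing completely at random. Confounding events tied to itch treatment may violate that last assumption. The point merits correction because the result gates both doses and most of the remedy is already planned.

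Separately, and adding no weight here, protocol 8.2 steps the increments weekly while SAP 2.7 steps through Weeks 2, 4 and 6.

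**What to change.** Before unblinding:
- Make MI combined by Rubin's rules the analysis that governs the primary test and the step-down. Move the fixed-value version to the sensitivity list.
- Extend the SAP 3.4.2 code, which shows one increment on treatment only, to several steps. Put earlier WI-NRS changes and as-randomized stratum in the imputation model.
- SAP 3.4.2 also says "Hence, there will be at least 1,000 random realizations of the responder status". If responder status is derived in each imputed data set, pool an estimate with its SE, for example the Mantel-Haenszel risk difference.
- State one stepping rule in both documents.

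**Cost.** SAP wording, a clarification of protocol 8.2 and a modest extension of the code. Power at difference 1, SD 2.9 and one-sided 5% falls from about 91% with complete data to 88–90% at 10% imputed and 85–90% at 20%.

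The missing-data assumption also changes. The present rule carries a subject's full deviation from the arm forward, whereas regression on earlier changes shrinks it. In checks with a true effect of 1 and response-dependent dropout, this moved the estimate by about 0.04–0.06 in either direction. The SAP should state that assumption openly.
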